### **1.3 Research hypothesis**

The vast majority of preclinical and clinical studies of RT and immunotherapy have only used one course of RT, either single fraction or fractionated. While this strategy is promising, especially based on exciting preclinical results showing dramatic synergy compared to RT or immunotherapy alone, there is reason to believe that the delivery of multiple RT courses may have an even more potent anti-tumor effect. When considering that RT is considered as an in situ tumor vaccine, in large part because it exposes the immune system to tumor neo-antigens, the rationale to use multiple RT courses is extrapolated from the response of the immune system to prophylactic vaccination against infectious disease. In the setting of vaccinations against infection a single inoculation is typically followed by multiple repeated inoculations (or “booster shots”) separated over time. Furthermore, vaccines against pancreatic cancer are commonly given with multiple boosters over several weeks to months.(Lutz, Yeo et al. 2011)

It has been well described that the first exposure of a foreign antigen leads to an initial antigen-specific immune response; subsequent exposure to the same antigen causes a more rapid and robust antigen-specific immune response(Owen, Punt et al. 2013). Likewise, exposure to the same antigen a third or even fourth time increases the efficacy of immune cells against that specific antigen and

decreases the time required for peak response. Therefore, the rationale for utilizing two courses of RT (instead of one) is that the first RT course may “prime” the immune system so that the second course may generate a secondary memory immune response that is more effective than the first. Another potential benefit of multi-course RT is that different tumor neo-antigens may be released from each of the two treated lesions, also leading to a more effective immune response by further expanding T-cell repertoire diversity.

The use of multi-course RT and immunotherapy was previously reported (Golden, Chhabra et al. 2015). Patients with metastatic cancer received 35 Gy in 10 fractions to two separate metastatic lesions with concurrent granulocyte-macrophage colony-stimulating factor (GM-CSF). Serious toxicities were uncommon. Immunomonitoring was not performed so the immunologic effect of the second RT course was not able to be specifically evaluated. Still, abscopal responses were observed in approximately 25% of patients. Given the development of modern immunotherapies such as immune checkpoint inhibitors there is reason to believe that an even higher rate of response may be seen if using multi-course RT and durvalumab.

#### **1.4 Rationale for conducting this study**

While a robust interaction between RT and immune checkpoint inhibitors has been repeatedly demonstrated in preclinical studies and has been suggested in clinical reports, it remains unclear what the optimal delivery for RT is to promote an anti-tumor immune response. There is ongoing investigation to determine what the appropriate number of fractions and the dose per fraction should be; this likely varies between tumor types and is dependent on the specific immunotherapy being used in combination.

Another question is whether treating several lesions with RT can lead to a strong immune response compared to treating a single lesion with a single course of RT. While multi-course RT may effectively control tumors, there are concerns about the added toxicity of RT and immunotherapy. Both can lead to inflammation-related adverse effects including colitis, hepatitis, and pneumonitis. While it does not appear that combining one or multiple courses of RT with immunotherapy results in an unacceptably high incidence of significant toxicity, further evaluation is needed. Therefore, this study will first evaluate the safety of combining sequentially giving ionizing radiation to 2 lesions with concurrent durvalumab, and if it is well tolerated, will continue to evaluate treatment efficacy.

The radiation dose for the lesions is a dose that is commonly used in studies that combine radiation and immunotherapy. This dose has been shown to result in abscopal responses with immunotherapy.

## **1.5 Benefit/risk and ethical assessment**

Patients with metastatic pancreatic cancer have an extremely poor prognosis, especially those who have progressed through first-line chemotherapy. These patients are clearly in need of novel therapies for disease control. The combination of RT and immunotherapy has the potential to provide significant benefit to these patients by at least prolonging the time to further disease progression, and also possibly causing significant tumor regression. While this is expected to be well tolerated, there is the potential for increased adverse effects over what has been observed using durvalumab monotherapy. RT may have similar adverse effects as durvalumab based on the region of the body receiving radiation dose. For instance, RT to a lung metastasis could lead to pneumonitis while RT To a liver metastasis could lead to hepatitis, both of which may also be seen with durvalumab.

## **2. STUDY OBJECTIVES**

### **2.1 Primary objective**

**2.1.1** The primary objective will be to evaluate whether the combination of RT and durvalumab improves median PFS compared to historical control in metastatic pancreas cancer patients who have progressed through first-line chemotherapy. PFS is defined as the time from the date of durvalumab initiation to the date of pancreatic cancer progression or death, whichever occurs first. This is a clinically relevant and appropriate endpoint for a phase II trial and since there are no prior studies

using immune checkpoint blockade with concurrent RT for metastatic pancreatic cancer will allow for historical comparison to PFS using second-line chemotherapy.

## **2.2 Secondary objective(s)**

- 2.2.1** To evaluate the toxicity profile of durvalumab and RT in metastatic pancreas cancer patients who have progressed through first-line chemotherapy and receive RT and durvalumab.
- 2.2.2** To evaluate OS in metastatic pancreas cancer patients who have progressed through first-line chemotherapy and receive RT and durvalumab.
- 2.2.3** To evaluate the best overall response rate (ORR) by RECIST 1.1 in metastatic pancreas cancer patients who have progressed through first-line chemotherapy and receive RT and durvalumab.
- 2.2.4** To evaluate the clinical benefit rate (CBR) by RECIST 1.1 in metastatic pancreas cancer patients who have progressed through first-line chemotherapy and receive RT and durvalumab.
- 2.2.5** To evaluate the time to in-field progression in metastatic pancreas cancer patients who have progressed through first-line chemotherapy and receive RT and durvalumab.
- 2.2.6** To evaluate the quality of life (QOL) as measured by questionnaires EORTC QLQ-C30 and EORTC QLQ-PAN26 in metastatic pancreas cancer patients who have progressed through first-line chemotherapy and receive RT and durvalumab.

## **2.3 Exploratory objectives**

Hypothesis-generating post-hoc analysis will be carried out since our study will not be powered to formally test pre-defined subgroup analysis. The following will be explored:

### **2.3.1 Tumor PD-L1 expression**

PD-L1 expression, using Ventana assay with SP263 antibody, will be evaluated on archival (less than 3 years old) or freshly biopsied pancreatic tumor obtained prior to study entry. Pancreatic biopsy can be of either the primary tumor or a metastatic tumor. PD-L1 expression is not required for study enrolment, but a correlation between greater treatment response to

immune checkpoint blockade and baseline PD-L1 expression has been reported in other cancer types including melanoma and non-small cell lung cancer. Whether this correlation exists for pancreatic cancer has not been well described so therefore we will retrospectively evaluate whether baseline PD-L1 expression correlates with efficacy endpoints.

### **2.3.2 Peripheral blood levels of CD8 T cells, regulatory T cells (Treg), and myeloid derived suppressor cells (MDSC)**

CD8 T cells, Tregs, and MDSCs all play important roles in the mounted immune response against cancer. Cancer therapies like immunotherapy and RT are successful in large part because they cause an increase in cancer-specific CD8 T cell numbers while they decrease the activity and concentrations of Tregs and MDSCs. We will study whether the absolute levels and/or change in the levels of these cells in peripheral blood at various intervals before, during, and after treatment with durvalumab and RT are correlated with efficacy endpoints. Serum will be drawn for this analysis prior to starting durvalumab, after completion of RT to the first lesion, after completion of the RT to the second lesion, during week 8, and at the time the patient is taken off the study due to disease progression or unacceptable toxicity.

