**Sponsor: Miami Cancer Institute at Baptist Health, Inc.**

**Principal Investigator: [name].**

**Department of Radiation Oncology**

**[name]**

**[name]**

**Office: [contact]**

**Main: [contact]**

**[contact]**

## PROTOCOL SYNOPSIS

### Clinical Protocol

Study Title: Phase II trial of in situ tumor vaccination using durvalumab and “booster” radiation therapy in patients with metastatic adenocarcinoma of the pancreas who have progressed through first-line chemotherapy.
Protocol Number: ESR 15 11078
Clinical Phase: II
Study Duration: 4 years
Investigational Products:  Durvalumab will be supplied in glass vials containing 500 mg of liquid solution at a concentration of 50 mg/mL for intravenous (IV) administration.  Radiation therapy (RT) will be delivered to 2 radiographically distinct pancreatic cancer lesions with concurrent durvalumab.
Research Hypothesis: The combination of ionizing radiation and immunotherapy (durvalumab) is well tolerated and stimulates a clinically significant pancreas-cancer specific immune response.
Objectives:  Primary Objectives: The primary objective will be to evaluate whether the combination of RT and durvalumab can improve median PFS compared to chemotherapy historical control data in metastatic pancreas cancer patients who have progressed through first-line chemotherapy.  Secondary Objective(s): Secondary endpoints include evaluation of toxicity, overall survival, overall response rate, clinical benefit rate, and time to in-field progression.  Exploratory Objective(s): Hypothesis-generating post-hoc analysis will be carried out since our study will not be powered to formally test pre-defined subgroup analyses. The following will be explored: 

1. Is there any correlation between PD-L1 expression level from the initial biopsy and efficacy of durvalumab with RT?

2. Is there any correlation between durvalumab with RT with levels of CD8 T cells, regulatory T cells, or myeloid derived suppressor cells in the peripheral blood at various intervals before, during, and after therapy? Is there any correlation between changes in levels of these cells over time and efficacy?

3. Is there a correlation between CA19-9 level and progression free survival and radiographic response?

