**Schedule of study assessments: Screening and Treatment Period (12 months: maximum of 13 doses, last infusion week 49)**

Assessments to be performed at the times stipulated in the table and as clinically required in the management of the subject.	PD-L1 status evaluation	Screening	All assessments to be performed pre-infusion unless stated otherwise				
			Baseline	Every 2 weeks	Every 4 weeks	Every 8 Weeks	Every 12 weeks
Day	-42 to -1	-28 to -1	1	Day 1 of the week			
Week	-6 to -1	-4 to -1	0	2, 4, 6, 8, 10, 12, etc (±3 days)	4, 8, 12, 16, 20, etc	8, 16, 24, 32, 40 and 48 (±7 days)	12, 24, 36, 48
Liver enzyme panel f				X			
Serum Chemistry (complete clin chem. panel including Liver enzymes) f		X	X		X		
Thyroid function tests (TSH and fT3 and fT4) g			X		X		
Hematology f		X	X		X		
Urinalysis h		X			X		
Coagulation parameters i		X	As clinically indicated				
CA 19-9		X	X		X		
Blood collection for correlative studies m			X	Days 1 (same day as baseline), 15, 29, 52 (see also Appendices B and C for 30 day post last dose Durvalumab blood draw)			
Blood collection for Future Biomedical Research m,n			X	Days 1 ( same day as baseline), 52 (see also Appendices B and C for 30 post last dose Durvalumab day blood draw)			

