### **8.3.2 Blood samples for correlative studies**

Blood for correlative studies should be drawn at the time points detailed in the Schedule of Study Assessments (Pre-Treatment on Day 1, and on Days 15, 29, and 52). These specimens should be transported to the Protocol Support Laboratory at Miami Cancer Institute (See section 8.3.4). A 4 teaspoon blood sample will be required to fill two 10mL Sodium Heparin tubes. Sodium heparin tubes for this study are available from the Protocol Support Laboratory. Blood sample tubes to be inverted several times immediately after the blood draw. The tubes may be transported to the Protocol Support Laboratory at ambient Temperature. It is preferable for the research blood to arrive to the Protocol Support Laboratory within 1-2 hours of the blood draw.

Clinical Study Protocol  
Investigational Drug Substance: MEDI4736  
Study Number **ESR 15 11078**  
Edition Number **1.09**  
Date **01 Feb 2018**

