### **11.4 Efficacy Endpoints**

#### **Primary**

Clinical Study Protocol  
Investigational Drug Substance: MEDI4736  
Study Number **ESR 15 11078**  
Edition Number **1.09**  
Date **01 Feb 2018**

**Progression free survival (PFS):** Progression free survival is defined as the time from the initiation of durvalumab to the first documented disease progression per RECIST 1.1 or death due to any cause, whichever occurs first. If a patient recurs and is eligible for retreatment, then only the time to the initial recurrence will be included in the evaluation of PFS. Patients who are alive with no evidence of disease at the time of last contact will be censored at that date.

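### The off-study blood draw is timed by progression or end of treatment, so immune-cell change up to that draw can correlate falsely with PFS if a marker keeps drifting

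*Combined protocol and SAP*

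**What the plan says.** Section 2.3.2 sets out the analysis. On the marker side it covers both levels and changes: "We will study whether the absolute levels and/or change in the levels of these cells in peripheral blood". The question put to those measurements is whether the values found "at various intervals before, during, and after treatment with durvalumab and RT are correlated with efficacy endpoints". The section then lists the samples: "Serum will be drawn for this analysis prior to starting durvalumab", after each of the two RT courses, in week 8, and finally "at the time the patient is taken off the study due to disease progression or unacceptable toxicity". The Synopsis (exploratory objectives) asks the same thing in general terms: "Is there any correlation between changes in levels of these cells over time and efficacy".

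Section 11.4 fixes the clock for the main efficacy endpoint: "Progression free survival is defined as the time from the initiation of durvalumab to the first documented disease progression" or death.

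Other places time the draws differently. Section 8.3.2 gives "Pre-Treatment on Day 1, and on Days 15, 29, and 52". The Schedule of Study Assessments adds a last draw after treatment ("see also Appendices B and C for 30 day post last dose Durvalumab blood draw"), and Appendices B and C carry it at day 30 after the last dose.

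Section 11 gives no method for these markers: no landmark, no time-dependent covariate, no joint model, and no restriction of the correlation to draws at fixed times. Section 2.3 and the Synopsis label the work exploratory and post hoc.

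**The concern.** For a patient who leaves because of progression, the time from baseline to the off-study sample is close to that patient's PFS. The 30-day version in the schedule has the same property, because treatment duration sets when the last dose falls. The change in a marker over that interval contains (drift per month) × (months on study). If all patients share the same continuing drift, those with longer PFS show a larger change even when the marker has nothing to do with outcome. The absolute level at the last draw has the same problem, because it contains the same drift term.

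Section 2.3.2 expects effective treatment to raise CD8 cells and lower Tregs and MDSCs. A continuing trend of that kind, common to all patients, would create associations in the direction the investigators hope to see. At stake is the planned evidence linking on-treatment immune change to benefit, which bears on the research hypothesis of an immune response. An analysis meant to generate hypotheses could generate a false one.

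**Working it through.** **1. Inputs from the documents.** 39 patients, 18 per year, 26 months of accrual, 12 months of further follow-up, median PFS 3 months (benchmark) or 4.5 months (target), exponential survival (Sections 11.2.2 and 11.3). CT every 8 weeks (9.1.1). At most 13 doses, the last at week 48 (5.1.2). Fixed draws on Days 1, 15, 29 and 52 (8.3.2).

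**2. The plan's own figure.** Events needed = ((1.645 + 0.842)/ln 1.5)² = 37.6. The probability of an event with median 4.5, 26 months of uniform accrual and 12 more months is 0.961. So N = 37.6/0.961 = 39.1. Power at N = 39 is 79.9%, and 39/18 × 12 = 26.0 months. The stated 39 reproduces, and the marker analysis does not enter it.

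**3. Model for a marker with no link to outcome.** Change = b·S + e, where S is months from baseline to the last draw, e ~ N(0,1), and b is the drift in SD per month. The values of b are assumptions; the documents supply none.

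**4. Hand check, idealised case.** Progression is dated continuously, everyone gives a last sample, and time on study is capped at 12 months. With median 4.5, the exponential mean is 4.5/0.693 = 6.49. For S = min(T, 12):
- exp(−12/6.49) = 0.1575
- E(S) = 6.49 × (1 − 0.1575) = 5.47
- E(S²) = 2 × 6.49² × (1 − 0.1575 × 2.848) = 46.5
- SD(S) = √(46.5 − 29.9) = 4.07

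The correlation of change with S is b·SD(S)/√(1 + b²·SD(S)²). At b = 0.1 this is 0.407/√1.166 = 0.38, and at b = 0.2 it is 0.814/√1.663 = 0.63. Simulated Spearman values are 0.36 and 0.61, with two-sided 5% rejection in about 62% and 99% of trials.

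**5. Closer to the plan.** Progression is dated at 8-week scans and treatment is capped at week 48. Two further assumptions are not in the documents: 25% of PFS events are deaths with no off-study draw, and 10% of patients leave for toxicity. About 29 of 39 patients then give a last sample. False-positive rate over 3,000 runs per cell:

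| Drift (SD/month) | Off-study draw, median 3 | Off-study draw, median 4.5 | 30 days after last dose, median 3 | 30 days after last dose, median 4.5 |
|---|---|---|---|---|
| 0 | 4.7% | 4.5% | 4.5% | 4.9% |
| 0.05 | 11.9% | 13.9% | 11.7% | 14.8% |
| 0.1 | 31.0% | 40.2% | 32.5% | 43.1% |
| 0.2 | 79.6% | 90.9% | 82.5% | 92.9% |
| 0.3 | 97.4% | 99.7% | 97.7% | 99.6% |

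Mean Spearman correlation for the off-study draw at 0.1 and 0.2 is 0.27 and 0.49 (median 3), and 0.31 and 0.55 (median 4.5).

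**6. Confirmation lag.** Section 9.1.3 continues durvalumab until progression is confirmed at least 4 weeks later, so the off-study draw can fall after the PFS date. Allowing for this lowers the rates to about 28% at 0.1 and 76% at 0.2. A variant with a 4- or 8-week lag gave 24–27% and 66–71%.

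**7. Drift that stops.** If the drift levels off by week 8, the rate is 4.6–5.3% at every drift tried.

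**8. Landmark alternative.** Correlate change to the Day 52 draw with PFS counted from Day 52, among patients still progression-free. The rate is 4.2–5.6% and the mean correlation about 0 for drifts from 0 to 0.5. About 36–37 of 39 patients remain. With continuously dated progression, 1 − 2^(−1.71/4.5) = 23% to 1 − 2^(−1.71/3) = 33% would have had an event before Day 52 (52/30.44 = 1.71 months).

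**The case against.** The strongest reply is that Section 2.3.2 names no test and no pairing. Change to the off-study draw, tested against PFS by Spearman correlation, is only one of many analyses the text allows, and the efficacy endpoints also include ORR and CBR. That is correct, and the rates above belong to that one pairing. Even so, the section names the off-study draw as a sample for this analysis, so an outcome-timed input is part of the stated plan and not merely a missing detail.

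A second reply is that the work is exploratory and no alpha or decision rests on it. That limits the consequences. It does not excuse a method that can create an association, because the exploratory label concerns power and pre-specification, not bias.

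A reader might go further than the documents allow in five ways:
- **Any drift on treatment gives a false association.** It does not. The drift must continue over the months in which patients leave. RT ends around Day 31, and a shift that settles by week 8 does no harm.
- **A false positive is near certain.** Rates of 62% and 99% need continuously dated progression and a last sample from every patient, including those who die.
- **The last-draw interval is the PFS time.** It tracks PFS closely but is not identical. Toxicity exits, the confirmation lag and treatment beyond confirmed progression all loosen the tie.
- **Many patients will have had their PFS event before the fixed draws.** The first scheduled scan is at week 8, after Day 52, so only early deaths, unscheduled scans and the scan window create such cases.
- **All the immune data are compromised.** Within-patient description of cell levels over time and the baseline PD-L1 analysis do not depend on this interval.

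**Conclusion.** The concern holds in a limited form. The off-study or 30-day post-dose draw is timed by the outcome or by treatment duration, it is a named input to the efficacy correlation, and nothing in Section 11 or Appendices B and C breaks the link. For a marker with no effect, the false-positive rate at a nominal 5% is about 11–15% at a drift of 0.05 SD per month, 28–41% at 0.1 and 76–91% at 0.2. Other choices of confirmation lag and draw timing move the last two ranges to 24–43% and 66–93%. The rate is about 5% if the drift stops by week 8.

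These figures rest on assumed drift sizes, a linear drift common to all patients, and assumed shares of deaths without a draw and of toxicity exits. The primary PFS test, N = 39 and the toxicity stopping rule are unaffected. This is an inexpensive improvement to an exploratory analysis, not a threat to the trial's main conclusion.

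**What to change.** In Section 2.3.2 and the Synopsis:
- Base any association of marker level or change with efficacy on the fixed-time draws only (Days 1, 15, 29 and 52).
- For each post-baseline draw, include patients alive and progression-free at that draw and count PFS and OS from it. A time-dependent Cox model or a joint model is an acceptable alternative.
- Report the off-study or 30-day post-dose draw descriptively only.
- Apply the same rule to serial CA 19-9 against PFS. This follows by analogy, since CA 19-9 is also drawn every 4 weeks and 30 days after the last dose; it was not calculated separately.

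Reconcile the draw times first. Section 2.3.2 places draws after completion of each RT course, in week 8 and at going off study. The Schedule, Section 8.3.2 and Appendices B and C give Days 15, 29, 52 and 30 days after the last dose. Under Section 5.2.2, Days 15 and 29 are the first days of the two RT courses, so they do not match draws after completion.

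The cost is a few sentences of analysis wording plus that reconciliation, with no extra samples. Patients with an event before a landmark drop out of that one comparison: about 2 or 3 of 39 at Day 52 with scan-dated progression, more if progression is found between scans. Marker changes after Day 52 would not be tested against PFS unless a time-dependent or joint model is used.
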